### 3. INTRODUCTION AND BACKGROUND INFORMATION

#### 3.1. Background

There are daily increasing numbers of Severe Acute Respiratory Syndrome (SARS) Coronavirus 2 (SARS-CoV-2) infected individuals globally and reports on impact / mortality vary constantly. As of 23 July 2020, over 15 million documented cases were reported worldwide of which more than 619,000 died ([World Health Organization \[WHO\] 2020](#)). Clinical manifestations of Coronavirus Disease-19 (COVID-19) vary, with approximately 5% of patients having critical manifestations (such as respiratory failure, septic shock, and/or multiple organ dysfunction) and 17-35% of hospitalized patients being treated in an intensive care unit (ICU), of whom 29-91% require invasive mechanical ventilation ([Wiersinga et al. 2020](#)).

The main COVID-19 characterizing clinical features are age greater than 50 years and presence of comorbidities such as hypertension and diabetes, whereas main laboratory findings show hepatic and renal dysfunction in the presence of leukopenia, lymphopenia, increase of D-dimers, and strong inflammatory cytokine activation ([Guan et al. 2020](#); [Huang et al. 2020](#); [Liu et al. 2020](#); [Garg et al. 2020](#); [Wiersinga et al. 2020](#)). Elevated D-dimer values have been shown to be strongly associated with poorer prognosis. It is also reported that the complement cascade is highly activated ([Gao et al. 2020](#)). One hallmark of progressed disease in patients who become severely diseased is the association of blood neutrophil increases with the disease severity, and neutrophil infiltration in the heart and liver.

Monoclonal antibodies directed against key inflammatory mediators, such as interleukin 1 and 6 and complement factor 5a (C5a), aim to modulate the overwhelming inflammatory response following SARS-CoV-2 infection, thereby preventing organ damage ([Wiersinga et al. 2020](#)). These targeted immunomodulatory agents are currently being evaluated for the management of COVID-19 and may prevent disease progression in hospitalized patients.

#### 3.2. Study Rationale

##### 3.2.1. Drug Profile

IFX-1 is a chimeric immunoglobulin G4 (IgG4) monoclonal anti-human C5a antibody, which specifically binds to the soluble human complement split product C5a. IFX-1 has been demonstrated to block C5a-mediated biological effects with high efficacy in vitro. C5a is one of the most potent inflammatory factors, triggering innate immune responses and bridging to adaptive immune responses ([Dunkelberger and Song 2010](#)). In blood, C5 is cleaved to C5a by components of the classical and alternative complement pathway, and the coagulation pathway, whereas in tissue, factors of the alternative complement and the coagulation pathway factors play a major role in C5a generation ([Hess and Kemper 2016](#)).

### 3.2.2. Non-clinical and Therapeutic Studies

Non-clinical studies were conducted to assess pharmacological and toxicological aspects of IFX-1 and showed that IFX-1 was able to rapidly bind to its target, the human C5a, and achieve an almost complete blockade of C5a-induced biological effects. At the same time, cleavage of C5 and formation of the complement membrane attack complex was not disrupted in vitro.

IFX-1 did not demonstrate any cross-reactivity or bioactivity in species other than humans and non-human primates (Section 4.2 of the Investigator Brochure [IB]). Therefore, toxicology studies were only conducted in cynomolgus monkeys.

IFX-1 has been investigated in viral-induced lung injury in monkeys infected with the avian flu virus H7N9. It had been shown that the neutrophil influx into the lung as well as the lung damage could be greatly reduced by this therapeutic attempt. In addition, the viral replication was greatly reduced as well, which is believed to be an indirect effect ([Sun et al. 2015](#)). This research was in line with findings generated in an H5N1 model of disease in rodents ([Sun et al. 2013](#)). Since then, the role of complement and specifically C5a for viral-induced lung injury has become an accepted concept in basic research ([Wang et al. 2015](#)). The same research group then confirmed the role of the C5a/C5a-receptor signaling axis for viral replication, for lung neutrophil influx and damage in a mouse model of Middle East Respiratory Syndrome Coronavirus (MERS-CoV) ([Jiang et al. 2018](#)). Another group of researchers then confirmed the role of complement activation and made similar findings on viral replication inhibition and lung damage reduction in complement deficient mice in a SARS virus infection model ([Gralinski et al. 2018](#)). One finding of this study was that complement deficient mice (C3-/-) had significantly less infiltration of the lungs with neutrophils and monocytes, also confirming earlier findings in greater detail for SARS-CoV induced viral lung injury.

This body of research has led to the approval by the Chinese FDA of two ongoing trials in SARS-CoV-2 infected patients in China with the monoclonal anti-C5a antibody BDB-1 (S-FDA approval number 2020L00003). BDB-1 is generated from the InflaRx IFX-1 cell line which has been transferred and licensed to the InflaRx collaborator Beijing Diferengui Biotech Co. (BDB). BDB develops BDB-1 under their responsibility in China and InflaRx has all rights to any discoveries made by BDB-1 globally outside China, where InflaRx develops IFX-1 in the rest of the world. The BDB-1 trials are ongoing, however data of the first two open label treated patients were reported in context of a research article by [Gao et al. 2020](#) (see Section 3.2.4).

None of the Good Laboratory Practice-compliant studies in cynomolgus monkeys revealed relevant toxicological or safety concerns for IFX-1. During single-dose and repeat-dose administration of IFX-1 at doses of up to 50 mg/kg body weight in cynomolgus monkeys no direct IFX-1-related toxicological or adverse findings within an extended core battery of safety pharmacology assessments were observed. Results showed dose-related increases in systemic and maximum exposure in the investigated dose range of 1 to 50 mg/kg body weight. Anti-drug

antibodies (ADAs) were detected in 1 animal in the 26-week repeat-dose study. This animal died, most likely because of an ADA-mediated immune complex formation.

An overview of the non-clinical toxicology studies that were conducted with IFX-1 is available in Table 8 of the IB.

For further details, refer to Section 4 of the IB.

### 3.2.3. Experience in Humans

At the time of writing of Protocol Version 2.0, Phase II of the current study has been completed and all 30 enrolled patients have been treated (15 in Arm A [best supportive care (BSC) + IFX-1] and 15 in Arm B [BSC alone]) for up to 28 days. Relative change (%) from baseline to day 5 in oxygenation index was assessed as the primary endpoint along with additional clinical parameters until day 28. Relative change in the oxygenation index at day 5 showed no differences between treatment groups. However, IFX-1 treatment was associated with a lower 28-day all-cause mortality when compared to the BSC arm, along with trends in disease improvement, as evidenced by fewer patients experiencing renal impairment assessed by eGFR, more patients showing reversal of blood lymphocytopenia and a greater lowering of lactate dehydrogenase concentrations. In IFX-1-treated patients, pulmonary embolisms (PE) reported as serious adverse events (SAEs) were lower compared to the BSC arm. Also, a temporary increase of D-dimer levels, as potential expression of induction of blood clot lysis, was detected in the first days after initiation of IFX-1 treatment.

Over a treatment period of 28 days, patients in the IFX-1 arm received a maximum of 7 doses of 800 mg IFX-1 intravenously (IV) on separate days. At randomization, 18 patients (60%) were intubated, and 12 patients (40%) had other oxygen supply. A higher number of patients with 2 or more comorbidities associated with increased COVID-19 mortality were reported in the IFX-1 treatment arm compared to the BSC arm. Twenty-eight-day all-cause mortality in the IFX-1 treatment arm was 13% (2 out of 15) versus 27% (4 out of 15) in the BSC arm. In the BSC arm, 4 patients died of COVID-19-induced multi-organ failure, and 3 of them had PE reported as SAEs. In the IFX-1 arm, one patient died after an acute ventilator tube complication (leakage) and one patient with a history of severe chronic obstructive pulmonary disease died of pulmonary failure. Serious AE rates were comparable between groups, but the rate of PE reported as SAEs was substantially lower in the IFX-1 treatment group. Upon review of the safety data, the independent data safety monitoring board has recommended continuation of the trial into Phase III.

IFX-1 is also being developed for the treatment of other inflammatory diseases. Five clinical studies in humans have been completed so far. One Phase I study in healthy volunteers (Study IFX-1-P1.1) and 4 Phase II studies: 1 in patients with early septic organ dysfunction (Study IFX-1-P2.1), 1 in patients undergoing complex cardiac surgery (Study IFX-1-P2.2), and 2 in patients with hidradenitis suppurativa (HS) (Studies IFX-1-P2.3 and IFX-1-P2.4; Section 5 of the [IB](#)).

To date, 391 subjects (26 healthy volunteers and 365 patients) have been treated in completed clinical studies of these other inflammatory diseases, of which 294 have received IFX-1 and 92 have received placebo. IFX-1 was safe and well tolerated, with no dose relationship in the safety findings. No specific adverse reactions emerged in clinical studies of single or multiple doses IFX-1 in healthy volunteers or patients with cardiac disease, sepsis, or HS.

Currently, 4 further Phase II studies are ongoing: 1 in patients with HS (Study IFX-1-P2.4; in final analyses), 2 in patients with granulomatosis with polyangiitis and microscopic polyangiitis (also referred to as anti-neutrophil cytoplasmic antibody-associated vasculitis; Study IFX-1-P2.5 and IFX-1-P2.6), and 1 in patients with pyoderma gangrenosum (Study IFX-1-P2.7).

Data are available from the interim analysis of the main period of the Phase II Study IFX-1-P2.4 in HS, where 141 patients were treated with IFX-1 in 4 different IFX-1 dose cohorts (400 mg and 800 mg every 4 weeks, 800 mg bi-weekly, and 1200 mg every 2 weeks) and 36 patients were treated with placebo. The total treatment duration in this study, which recently completed treatment, was 9 months. Treatment with IFX-1 was safe and well tolerated with rare occurrence of AESIs, defined as infusion reactions, including hypersensitivity or anaphylaxis, meningitis, meningococcal sepsis, and invasive infection. Four patients experienced AEs suggestive of hypersensitivity. The reactions were moderate, and treatment continued, if necessary with adequate prophylactic medication. Anti-drug antibodies during treatment were observed in a range of 5.6% to 12.9% with a trend towards increasing frequency with low dose and larger administration intervals.

### 3.2.4. Scientific Rationale for the Study

Neutrophil driven tissue and organ damage is known to play an important role in a wide array of acute inflammatory diseases. The mechanism leading to damage has been largely attributed to two mechanisms: 1) the release of granular enzymes and 2) the generation of so-called reactive oxygen species in which O2 radical formation elicits a damaging effect.

One of the strongest chemoattractant substances, which is also capable of inducing both mechanisms described above is the human complement split product C5a.

Earlier research by InflaRx has demonstrated that the anti-human C5a antibody IFX-1 could significantly reduce the neutrophil and macrophage infiltration in a model of viral (H7N9)-induced lung injury in monkeys ([Sun et al. 2015](#)). This was accompanied by a significantly reduced tissue damage in the lung of infected animals and also a significantly reduced viral replication when compared to mock-treated animals. The mechanism was then confirmed in a model of MERS-CoV-induced lung injury where similar findings were made by using an anti-C5a receptor antibody ([Jiang et al. 2018](#)) and in a model of SARS-CoV-induced lung injury by using complement C3 knockout mice ([Gralinski et al. 2018](#)). The latter study also provided evidence for a profound complement activation in SARS virus infections in animals. These studies all suggested a role of neutrophil driven lung damage, which was induced by generation of C5a in different viral-lung injury models, including SARS viruses.

Latest data from a collaborating research group in China demonstrated strongly and significantly elevated C5a levels in severely diseased COVID-19 patients when compared to mildly diseased patients ([Gao et al. 2020](#); [Carvelli et al. 2020](#)) and revealed evidence for a strong complement pathway driven activation of C5a in this disease. In addition, data from the first two severely diseased COVID-19 patients treated with the IFX-1 cell line derived anti-C5a antibody BDB-1, which InflaRx licensed to a collaborator in China, demonstrated clinical improvement in oxygenation index, fever reduction, and laboratory parameter normalization including liver enzymes and lymphocyte counts.

From a clinical perspective, various papers have confirmed that COVID-19 infected non-surviving patients demonstrated lung failure with close to 100% ([Zhou et al. 2020](#)) and that, in contrast to surviving patients, non-survivors demonstrated elevated white blood cell counts and neutrophils above the normal range ([Wang et al. 2020](#); [Gong et al. 2020](#)).

In summary, there is evidence that in COVID-19 patients who are severely affected, C5a activation occurs to a large extent and that neutrophil count elevation in blood is associated with bad outcome. These human data fit well to the scientific rationale developed in animal models of viral-induced lung injury that activated neutrophils attracted to the lung may cause viral-induced lung damage. First treatment attempts with the anti-C5a antibody technology developed by InflaRx (BDB-1) in severely affected COVID-19 patients provide further evidence for the scientific rationale.

The completed Phase II portion of the current trial was exploratory in nature and was not powered to show statistically significant differences in clinical endpoints. Relative change (%) from baseline to day 5 in the oxygenation index, chosen as the primary endpoint for Phase II, showed a large variability and dependency on patient positioning and intubation status which excluded this endpoint from being used in a confirmatory study. Phase III of the study is an adequately powered, placebo-controlled, double blinded phase evaluating standard of care (SOC) + IFX-1 versus SOC + placebo-to-match with 28-day all-cause mortality as the primary endpoint, an accepted regulatory primary endpoint for critical care studies.

At the time that Phase II of this study was initiated, there was no SOC established for this newly identified disease. The SOC to be utilized in Phase III of this study reflects the current understanding of the SOC for hospitalized patients with COVID-19, which includes venous thromboembolism (VTE) prophylaxis at a minimum, and may include other international and country-specific recommended treatments for COVID-19 per the locally adopted treatment recommendations.

### **3.2.5. Justification for Dose**

The aim for determining the dose and administration frequency for IFX-1 is to establish a pragmatic administration schedule for the COVID-19 patient population. IFX-1 dose and administration schedule was chosen based on prior pharmacokinetic (PK)/pharmacodynamic (PD) observations for IFX-1 trough values and blood C5a levels, dose-response assessment in

Study IFX-1 P2.4 in HS, and the described unprecedented high C5a levels in patients with severe COVID-19 related pneumonia ([Gao et al. 2020; Carvelli et al. 2020](#)). In a population PK/PD modelling study for IFX-1 based on the data of the 2 trials in HS patients, a reduction in C5a concentration was found to be dependent on all measures of drug exposure, with increasing exposure predicting a greater reduction in C5a.

The observed half-life of IFX-1 with a single dose of 800 mg was 3 to 4 days in Study IFX-1 P2.2 in patients undergoing complex cardiac surgery. Thus, an additional dose of 800 mg at Day 4, followed by weekly administration of 800 mg IFX-1 was chosen for Study IFX-1 P2.3 in patients with HS.

In Study IFX-1 P2.3 in patients with HS, 800 mg once-weekly IFX-1 was administered for up to 9 times including an additional dose of 800 mg at Day 4. This administration schedule resulted in IFX-1 trough concentrations of around 50 µg/mL and a decrease of elevated baseline C5a levels to approximately detection limit throughout the treatment duration in the majority of patients. This dosing regimen was well tolerated, with no new safety signals, and clinical improvement of HS was observed in some patients.

In another clinical study in HS (Study IFX-1 P2.4), 4 different dosing schedules were explored, of which the highest dose was 1200 mg every 2 weeks. Safety findings were similar in all dose groups, and similar to safety findings in previous studies, with no new specific AESIs.

Based on the above data, the dosing schedule of IFX-1 for this study includes an additional dose of 800 mg IFX-1 at day 2 in the established fractionated loading dose scheme, that foresees administration of 800 mg at days 1, 4, and 8. This additional dose has been chosen due to the reported high C5a levels in COVID-19 patients ([Gao et al. 2020](#)). Therefore, the entire dosing scheme contains up to 6 IFX-1 doses of 800 mg at days 1, 2, 4, 8, 15, and 22 (or less until hospital discharge). This regimen had been employed in Phase II of this study, leading to a lower death rate and supporting efficacy signals without any new signals of unknown toxicities ([Vlaar et al 2020](#)).

### 3.3. Benefit/Risk Assessment

IFX-1 is a chimeric IgG4 antibody that has the potential to elicit infusion reactions, including hypersensitivity or anaphylaxis. In animal studies, one unexplained death of a cynomolgus monkey retrospectively showed development of anti-IFX-1 antibodies. In clinical studies, few patients tested positive for anti-IFX-1 antibodies, and only mild to moderate signs of hypersensitivity reactions were occasionally observed so far (overall ADA rate in the range of 5% to 13%). In total, IFX-1 showed very good tolerability in clinical studies. The majority of observed AEs were attributed to the underlying diseases and IFX-1 AESIs occurred occasionally (see [IB](#) for details).

A summarized in Section 3.2.4, there is evidence that in COVID-19 patients who are severely affected, C5a activation occurs to a large extent and that neutrophil count elevation in blood is associated with worse outcomes.

Data from the interim analysis from the completed Phase II of the current study demonstrated that IFX-1 treatment was associated with a lower 28-day all-cause mortality when compared to the BSC arm, along with trends in disease improvement, as evidenced by fewer patients experiencing renal impairment, more patients showing reversal of blood lymphocytopenia, and a greater lowering of lactate dehydrogenase concentrations. In IFX-1-treated patients, PE reported as SAEs were lower compared to the BSC arm. Also, a temporary increase of D-dimer levels, as potential expression of induction of blood clot lysis, was detected in the first days after initiation of IFX-1 treatment.

Overall, the expected clinical benefit for patients suffering from COVID-19-related severe pneumonia outweighs the risks in relation to the mild to moderate side effects that have been attributed to IFX-1 so far.

## **4. OBJECTIVES AND ENDPOINTS**

### **4.1. Study Objectives**

#### **4.1.1. Primary Objectives**

The primary objective of Phase II was:

- To explore the effect of IFX-1 on COVID-19 related severe pneumonia (hypothesis generating)

The primary objective of Phase III is:

- To demonstrate the efficacy of IFX-1 to improve survival outcomes of severe COVID-19 pneumonia (confirmative)

#### **4.1.2. Secondary Objectives**

The secondary objectives of Phase II and Phase III are:

- To assess and define other parameters of efficacy
- To assess the safety of IFX-1

## 4.2. Study Endpoints

### 4.2.1. Phase II

#### 4.2.1.1. Primary Endpoint

The primary endpoint in Phase II was the relative change (%) from baseline (day 1 prior to study drug administration at  $\pm 1$ h of randomization) in oxygenation index ( $\text{PaO}_2 / \text{FiO}_2$ ) in supine position at day 5.

#### 4.2.1.2. Secondary Endpoints

The secondary endpoints in Phase II were:

- Number of patients (%) achieving an **Early Response** as defined as meeting ALL of the following criteria at day 7 after enrollment:
  - Patient alive and extubated OR oxygenation index  $\geq 300$  OR improvement of  $\geq 30\%$  from baseline
  - Temperature  $< 38^\circ\text{C}$  in absence of fever decreasing medication of at least 4h
  - White blood cell count within normal limit of local lab quantifications
- Number of patients (%) reaching a **Late Response** as defined by either being **discharged alive** from hospital until day 28 **OR** meeting ALL of the following criteria at day 28 of the trial
  - Patient alive and extubated
  - Patient discharged from ICU
  - Patient free of shortness of breath (respiratory rate  $< 20$ ) in absence of oxygen supply
  - Patient free of fever ( $< 37.6^\circ\text{C}$ )
- Relative change (%) from baseline (day 1 prior to study drug administration at  $\pm 1$ h of randomization) in oxygenation index ( $\text{PaO}_2 / \text{FiO}_2$ ) in supine position at day 3, 7, 9, and 11.
- All cause 28-day mortality (%)
- Frequency, severity, and relatedness to study drug of treatment-emergent adverse events (TEAEs) and SAEs

#### 4.2.1.3. Other Endpoints

The other endpoints in Phase II were:

- Change from baseline in alanine aminotransferase (ALT) and aspartate aminotransferase (AST)
- Change from baseline in troponin I adjusted to glomerular filtration rate
- Change from baseline in creatinine

- Change from baseline in lymphocyte counts
- Change from baseline in neutrophil counts
- Change from baseline in D-dimers
- Change from baseline in Glasgow Outcome Scale
- Time to reach ICU discharge criteria as defined by ALL of the three criteria below:
  - Alive and extubated
  - No need for continued (>3h per day) non-invasive ventilation
  - Free of vasopressor and inotropic therapy
- Assessment of complement activation parameters and plasma concentrations of IFX-1

#### **4.2.2. Phase III**

##### **4.2.2.1. Primary Endpoint**

Based on the preliminary interim analysis of efficacy data from Phase II, the primary endpoint chosen for Phase III is 28-day all-cause mortality.

##### **4.2.2.2. Secondary Endpoints**

The secondary endpoints in Phase III are:

- 60-day all-cause mortality (proportion of patients deceased until Day 60)
- Proportion of patients with an improvement in the 8-point ordinal scale (Appendix 7) (day 15, day 28)
- Proportion of patients developing acute kidney failure (eGFR < 15 mL/min/1.73m^2, assessed by the CKD-EPI equation requiring race information) during ICU stay and at day 28
- Proportion of patients free of any renal replacement therapy within 28 days upon randomization
- Frequency, severity, and relatedness to study drug of serious and non-serious TEAEs

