## CONFIDENTIAL

Screening/ Randomization	Treatment Period IMP administration and assessments as long as in ICU / Hospital									Follow-up Period (Telephone possible)	
	Week 1			Week 2	Week 3	Week 4	Week 5	Any time		FUV	
	Screening not more than 24h before randomization	Day 1 (at-or up to 24h after random- ization)	Day 2	Day 4	Day 8	Day 15	Day 22	Day 28 (if still in hospital)	ICU discharge	Hospital discharge	Day 28
Endpoint Assessments											
Organ support (renal replacement therapy, ECMO, mechanical ventilation)							X				
Extubation and re-intubation date(s)						X					
Ordinal scale evaluation f	X				X	X	X	X	X	X	
Survival status					X					X	X
Quality of life (EQ-5D)											X
Glasgow Outcome Scale											X
Safety Assessments											
Safety laboratory tests g	X	X	X	X	X	X	X	X	X		
Creatinine h	X	X	X	X	X	X	X	X	X		
Vital signs i		X	X	X	X	X	X	X	X		
Adverse events j	X				X					X	X
Physical examination l	X	X	X	X	X	X	X				
Concomitant medications and procedures						X					
12-lead ECG	X							X			
PK/PD Assessments (Country-specific)k											
IFX-1 sample	X			X				X			

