- g Day 1 assessment has to be done prior to IMP administration only, if more than 12 h elapsed between screening assessment and IMP administration. Safety laboratory tests include hematology (hemoglobin, hematocrit, platelet count, red blood cell count, red blood cells (MCV), white blood cell count with differentials (neutrophils, lymphocytes, monocytes, eosinophils, basophils), coagulation parameters (activated partial thromboplastin time [aPTT], prothrombin time [PT], D-dimer), blood chemistry (ALT, AST, lactate dehydrogenase [LDH], total bilirubin, and c-reactive protein [CRP]) (see Appendix 1, Table 4). Blood samples for safety laboratory analysis should be obtained at indicated days during routine sampling (one representative value, if taken more than once a day).
- h Creatinine assessment should be obtained at indicated days during routine sampling (one representative value, if taken more than once a day). Day 1 assessment has to be done prior to IMP administration only, if more than 12 h elapsed between screening assessment and IMP administration.
- i Vital signs (core body temperature, heart rate, respiratory rate, blood pressure [diastolic and systolic]) will be assessed at indicated visits at pre-dose within 1h before administration of IMP (one representative measurement closest to IMP administration) and at further time points whenever medically indicated. Blood pressure and heart rate measurements will be assessed with an intra-arterial catheter, or a completely automated device. Manual techniques will be used only if an automated device is not available.
- j Adverse event reporting will follow special considerations for the ICU setting as described in Section 9.1 ff and Appendix 3.
- k PK/PD sampling will be conducted at selected countries/sites. PK/PD samples will be taken within 1h before administration of IMP.
- l Day 1 assessment has to be done prior to IMP administration only, if more than 24 h elapsed between screening assessment and IMP administration.

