#### 10.2.3.2. Secondary Efficacy Analyses

The secondary efficacy analyses will be performed based on the FAS.

The first secondary efficacy endpoint will only be addressed with statistical hypothesis tests if the primary endpoint is statistically significant using the full overall 2.5% one-sided alpha. If the first secondary endpoint is also statistically significant, the full 2.5% one-sided alpha will be passed to the 4 remaining secondary endpoints. Multiplicity in the secondary endpoints will be addressed with the fallback method. 60-day mortality will be analyzed similar to 28-day mortality and the other secondary endpoints will be evaluated using a logistic regression model with the explanatory variables randomized treatment arm (Arm B versus Arm A) and age for:

1. 60-day all-cause mortality
2. Proportion of patients with an improvement in the provided 8-point ordinal scale at day 15 (at least one score point lower than at randomization)
3. Proportion of patients with an improvement in the provided 8-point ordinal scale at day 28 (at least one score point lower than at randomization)
4. Proportion of patients developing acute kidney failure ( $eGFR < 15 \text{ mL/min}/1.73\text{m}^2$ ) during ICU stay and at day 28
5. Proportion of patients free of any renal replacement therapy within 28 days upon randomization
- 6.

The ordering of the secondary endpoints 2 to 5 for hypothesis testing will be as in above mentioned list. The full 2.5% one-sided alpha for the fallback method will be attributed to the 4 secondary endpoints in the following way 2%, 0.2%, 0.2%, and 0.1%. If the preceding hypothesis test is not significant, subsequent tests will be performed at the aforementioned alpha level. If tests are significant, the alpha is added to the subsequent hypothesis test (e.g., if the primary hypothesis test is significant and secondary endpoints 1-4 are all significant, the fifth secondary endpoint will be tested at an alpha of 2.5%; if the fourth secondary endpoint is not significant, the fifth secondary endpoint will be tested at an alpha of 0.1%).

The primary endpoint as well as all secondary endpoints will also be evaluated as censored time to event variables by Kaplan-Meier type methods. Kaplan-Meier analyses will be performed comparing the two treatment arms overall and within the following stratifications:

- Stratification by site
- Stratification by country

- Stratification by sex
- Stratification by age
- Stratification by comorbidities

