##### *Patients Alive and Free of Respiratory Failure*

Patients achieving 8-point ordinal scale score 3 or below (patients alive and free of respiratory failure) at day 15 and day 28 are defined as alive and free of respiratory failure at the respective study day. The corresponding endpoint will be analyzed using logistic regression with explanatory variables age and treatment group.

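### Secondary endpoint 4 can miss kidney failure that is dialysed before a counted eGFR falls below 15, and secondary endpoint 5 has no survival condition, so the renal conclusion is blurred when IFX-1 lowers mortality

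*Combined protocol and SAP*

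**What the plan says.** All references are to protocol Version 4.0.

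**Endpoint definitions.** Section 4.2.2.2 defines the fourth-ranked secondary endpoint as "Proportion of patients developing acute kidney failure (eGFR < 15" mL/min/1.73m², completed by "assessed by the CKD-EPI equation requiring race information) during ICU stay and at day 28". The fifth, in Section 10.2.3.2, is "Proportion of patients free of any renal replacement therapy within 28 days upon randomization". No text counts RRT as kidney failure, sets aside creatinine measured on RRT, or says how death is scored for either endpoint.

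**Data.** Table 2, footnote h: "Creatinine assessment should be obtained at indicated days during routine sampling (one representative value, if taken more than once a day". Read in order, the creatinine row has entries at screening, days 1, 2, 4, 8, 15, 22 and 28, and ICU discharge. The day 28 column applies to patients still in hospital. RRT is recorded separately under "Organ support (renal replacement therapy, ECMO, mechanical ventilation" and in Section 8.2.2.1; survival is covered in Section 8.2.2.3.

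**Analysis.** Section 10.2.3.2 says that "the other secondary endpoints will be evaluated using a logistic regression model with the explanatory variables randomized treatment arm" and age. It adds: "The primary endpoint as well as all secondary endpoints will also be evaluated as censored time to event variables by Kaplan-Meier type methods". Endpoints 2 to 5 receive alpha only if 28-day mortality and then 60-day mortality are significant. Their starting shares are 2%, 0.2%, 0.2% and 0.1%, and a significant test passes its alpha on.

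**Deferral.** Section 10.2.3 leaves exact endpoint definitions and missing-data rules to the SAP. No Phase III SAP text is in the document reviewed.

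**The concern.** RRT removes creatinine, and it may be started for reasons other than a very high creatinine. Take a patient with eGFR 22 on day 8 who becomes anuric and starts RRT on day 10. The next scheduled creatinine, on day 15, is a dialysed value. If no other counted value falls below 15, endpoint 4 classes this patient with those whose kidneys never failed.

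The protocol itself does not treat creatinine as sufficient. Section 9.2.1 lists new anuria beside raised creatinine as a life-threatening kidney event. Appendix 7 places RRT in a ventilated patient at score 7, the worst state short of death. Section 6.2.2 excludes recent, chronic and imminently expected RRT, so the RRT seen in the trial is mostly new.

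The window adds a second gap. A failure on the ward on day 20 lies outside the ICU stay, so it counts only if eGFR is still below 15 at day 28.

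Endpoint 5 has a different gap. A patient who dies on day 4 without RRT has, literally, received none within 28 days. Elsewhere the protocol deals with death explicitly. Patients with an ordinal score of 3 or below "are defined as alive and free of respiratory failure at the respective study day", and time to first extubation treats death as a competing event (both in Section 10.2.3.3).

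At stake is whether the two renal tests can show a renal effect, and whether their result can be read as one.

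**Working it through.** **Method.** Pooled two-proportion z-test, n = 180 per arm, one-sided, without continuity correction unless stated:

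power = Φ{[Δ − z·√(2p̄(1−p̄)/n)] / √[(p₁(1−p₁)+p₂(1−p₂))/n]}, with z = 1.960 at 2.5%, 2.878 at 0.2% and 3.090 at 0.1%. Age adjustment is ignored.

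**The plan's own figures.** For 30% against 15% mortality (Section 10.2.1) the formula gives 92.9%. With a continuity correction (Δ reduced by 1/180) it gives 91.0%. The stated 90% is therefore reasonable and not in dispute. The fallback shares sum correctly: 2 + 0.2 + 0.2 + 0.1 = 2.5%.

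**Alpha available.** Endpoint 4 starts at 0.2% and can reach at most 2 + 0.2 + 0.2 = 2.4%. Endpoint 5 starts at 0.1% and reaches 2.5% only if endpoints 2, 3 and 4 all succeed. Power is therefore shown at both ends. The 2.5% column for endpoint 4 slightly exceeds its 2.4% maximum, where power with full detection is 58.5% instead of 59.2%.

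**Endpoint 4: patients misclassified.** Assume RRT in 20–30% of patients, of whom 30–70% never show a counted eGFR below 15. Then 0.20 × 0.30 = 6% to 0.30 × 0.70 = 21% are misclassified, or about 22 to 76 of 360.

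**Endpoint 4: power.** Assume true rates of 30% and 20%, and that a share d of events is detected in both arms.

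| d | observed rates | power at 2.5% | power at 0.2% |
|---|---|---|---|
| 100% | 30% vs 20% | 59% | 24% |
| 70% | 21% vs 14% | 42% | 13% |
| 50% | 15% vs 10% | 30% | 7% |
| 30% | 9% vs 6% | 19% | 4% |

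First row, 2.5%: √(2 × 0.25 × 0.75/180) = 0.0456; √((0.21 + 0.16)/180) = 0.0453; (0.10 − 1.960 × 0.0456)/0.0453 = 0.23; Φ = 0.59.

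**Endpoint 5: proportions.** Mortality of 30% and 15% is the protocol's. Assume RRT in 15% (placebo) and 10% (IFX-1) of survivors, and a share f = 20–60% of deaths without RRT.

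- As written, placebo: 0.70 × 0.85 + 0.30f = 65.5% (f = 0.2) to 77.5% (f = 0.6).
- As written, IFX-1: 0.85 × 0.90 + 0.15f = 79.5% to 85.5%.
- Alive and RRT-free: 59.5% against 76.5%.
- Deaths scored as successes: 54f = 11 to 32 on placebo and 27f = 5 to 16 on IFX-1.

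| Definition | difference | power at 2.5% | power at 0.1% |
|---|---|---|---|
| As written, f = 0.2 | 14 points | 85% | 45% |
| As written, f = 0.6 | 8 points | 50% | 13% |
| Alive and RRT-free | 17 points | 94% | 65% |

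**How much of the 17 points is renal?** Set RRT to 15% of survivors in both arms. Alive and RRT-free becomes 59.5% against 0.85 × 0.85 = 72.25%. The difference is 12.75 points, or 12.75/17 = 75% of the gain, from mortality alone.

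**The case against.** **Deferral.** Exact definitions are left to the SAP. Scoring an early death as RRT-free follows from a missing condition, not from a stated rule, so the SAP may already settle it. This stands as a limit on certainty. The protocol wording is still what endpoints 4 and 5 rest on here, and nothing in the document overrides it.

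**The gate.** A reader might infer that endpoint 5 could confirm a false renal benefit if IFX-1 caused early deaths. Section 10.2.3.2 rules that out: a drug that raised mortality would have to pass two one-sided mortality tests before endpoint 5 was tested. Such a benefit could appear only descriptively.

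**Not every dialysed patient is missed.** A counted eGFR below 15 before RRT makes the patient a case. Section 8.2.3.2 allows extra tests and requires clinically significant values from them in the eCRF. Whether these feed endpoint 4 is unspecified, not excluded.

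**Separate endpoints can be defended.** One endpoint measures biochemistry and the other treatment, and a dialysed patient is a failure on endpoint 5. The literal endpoint 5 is also a coherent quantity: one minus the cumulative incidence of RRT with death as a competing event. But that describes RRT use, not a good outcome, and it improves when patients die before RRT.

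**Alive and RRT-free mainly re-tests mortality.** This stands. The 94% must not be read as power for a renal effect.

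**Conclusion.** The point holds as a defect in two confirmatory secondary definitions, worth correcting before unblinding. Endpoint 4 loses patients who start RRT before any counted eGFR is below 15 and then have only dialysed values, and it can miss failure on the ward before day 28. Endpoint 5 literally scores death without RRT as success. Formal testing happens only when IFX-1 has lowered mortality, and that is when the literal endpoint 5 works against IFX-1.

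The size is illustrative. Only the mortality rates, sample size and alpha shares come from the protocol. RRT incidence, the share missed, the true kidney-failure rates and the share of deaths without RRT are assumptions. Under them, endpoint 4 drops from 59% to 42/30/19% power at 2.5%, and from 24% to 13/7/4% at 0.2%. Endpoint 5 has 50–85% against 94% at 2.5%, and 13–45% against 65% at 0.1%. The 2.5% figures are a best case, because that alpha depends on every earlier test succeeding.

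The documents do not support reading this as a threat to the primary analysis or as a route to a confirmed false renal claim.

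**What to change.** Change Sections 4.2.2.2 and 10.2.3.2, with the synopsis to match, and carry the wording into the SAP before unblinding.

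- **Endpoint 4:** acute kidney failure is any creatinine-based eGFR below 15, or start of RRT, from randomization to day 28, in the ICU or not. Values taken on RRT are not used to rule it out.
- **Endpoint 5:** alive at day 28 and free of any RRT from randomization to day 28. Report it with its components (death, RRT) and with the cumulative incidence of RRT, taking death as the competing event, as Section 10.2.3.3 already does for extubation.

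The SAP should also say whether unscheduled creatinine values count. The logistic model, test order and alpha shares can stay.

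Cost: wording and programming only, since RRT, creatinine and survival are already collected. There are two downsides. Endpoints 4 and 5 will overlap more. Endpoint 5 will largely reflect mortality, so it must not be read alone as a renal effect.
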